### Research Procedures

All patients will be provided a FitBit Versa 3\* device which will be worn continuously during the pre-operative and intra-operative period. If randomized into one of two virtual reality groups, they will also be provided one pair of SmileyScope VR goggles\* to wear. Physiologic data associated with subjective pain and peri-operative anxiety is of interest to the study team (i.e., heart rate, skin

temperature, oxygen saturation). Physiologic data during the pre-operative period will be used as a baseline to measure changes in intra-operative pain. Pre-operative anxiety will be assessed via a modified six-item State-Trait Anxiety Inventory (STAI-6) anxiety questionnaire scored from 0-24. The STAI-6 has been previously validated in the assessment of anxiety in surgical patients. Physiologic data will be correlated with subjective measures of average or maximal intra-operative pain (numeric pain scale; 0-10) and anxiety (STAI-6; 0-24). Effectiveness of the VR goggles in managing intraoperative pain will also be assessed by post-operative satisfaction surveys.

\*Participants will not be held responsible for damaged or lost equipment provided by the study team. If any of the provided research hardware is damaged or deemed missing by the participant during the study period, replacements will be provided. Participants will be asked to return the FitBit Versa 3 and SmileyScope device after the procedure. The device will have a generic account associated with it, and data will be extracted from the device immediately after the procedure and deleted from the device.

## Time Period of Data under Review

Data will be collected at enrollment, and during the procedure. Information will be kept for 3 years. De-identified data will be stored in a secure database for the duration of the study.

## 6) Data and Specimen Banking

The following datapoints will be collected at initial clinic visit:

- Medical Record Number
- Age
- Date of Birth
- Sex
- Race/Ethnicity
- Marital Status
- Medical History
- Medications

The following data will be collected pre-procedure:

- Numerical anxiety scale survey (Modified 6-term STAI-S anxiety scale)
- Baseline pain measure
  - o “Please rate your current pain from 0 (no pain) to 10 (worst pain imaginable).”
- Physiologic data provided by FitBit Versa 3 – Data collected pre-procedure in waiting room. Data will be collected continuously during the time the patient is wearing the device. Data will be extracted from the FitBit after the procedure is finished and the patient has left.
  - o Heart Rate
  - o Oxygen saturation
  - o Skin temperature

The following data will be collected post-procedure:

- Length of procedure (start and end time)

- Numerical anxiety scale survey (Modified 6-term STAI-S anxiety scale)
- Numerical pain scale survey:
  - o Maximum pain felt during the procedure: "Please indicate the highest intensity of pain during the procedure on a scale of 0 (no pain) to 10 (worst pain imaginable)"
  - o Average pain felt during the procedure: "Please indicate the average intensity of pain during the procedure on a scale of 0 (no pain) to 10 (worst pain imaginable)"
- Post-procedure satisfaction:
  - o "How satisfied were you with today's procedure?"
  - o "If your urologist was using VR, would you be more or less likely to have the procedure?"
  - o "If your urologist was using VR, how likely would you be to recommend them to a friend undergoing the same procedure?"
  - o "How helpful was VR in managing your vasectomy today?"
  - o "Do you have any comments on today's procedure?"
    - Free text form for patient comments
  - o All questions will be answered via a 5-point Likert Scale as below:
    - 5 – Very Satisfied
    - 4 – Somewhat Satisfied
    - 3 – Neither Satisfied nor Dissatisfied
    - 2 – Somewhat Dissatisfied
    - 1 – Very Dissatisfied
    - 0 – Not applicable / Decline to Answer
- Physiologic data provided by FitBit Versa 3 - Data collected during the procedure and after the procedure in the waiting room
  - o Heart Rate
  - o Oxygen saturation
  - o Skin temperature
- Adverse effects associated with goggles. Adverse effects are anticipated to be mild and not more than minimal risk. Patients can remove headsets at any time they wish, and adverse effects are anticipated to resolve with headset removal. Most common adverse effects include dizziness and nausea.

De-identified data will be stored in a secure database for 3 years.

- **Secure Storage:** Data will be housed in a HIPAA-compliant secure storage system, like REDCap or Box, within the University of Miami network with access restricted to approved members of the research team.
- **Limited Access:** Private identifiable information will be accessible only to IRB approved study team members with current IRB training.
- **Storage of Physical Records:** Physical records will be maintained for this study at a secure location where access is limited to approved personnel. The records will not be removed from University of Miami premises.
- **Storage of Specimens:** Specimens will be maintained for this study at a secure location where access is limited to approved personnel. The specimens will not be removed from University of Miami premises.

- **Retention/Destruction of Study Materials:** Study data/materials will be kept and/or destroyed according to applicable policy.

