## 2) Objectives

The primary objective of this study is to assess the feasibility of using virtual reality goggles to modulate pre-operative anxiety and intraoperative pain during vasectomy. Feasibility will be measured via the following parameters:

Pain will be quantified in the following manner:

- Pre-operative, intra-operative, and post-operative physiological parameters (heart rate, temperature, oxygen saturation) measured by FitBit Versa 3 device
- Numeric pain scale pre- and post-vasectomy

Anxiety will be measured in the following manner:

- Pre- and post-vasectomy State-Trait Anxiety Inventory (STAI) anxiety score

Feasibility will be further measured via subjective post-procedure satisfaction surveys. Further discussion of data analysis is detailed in the Research Procedures and Data and Specimen Banking sections of this protocol.

The secondary goal of this study will be to evaluate the effectiveness of interactive virtual reality versus static virtual reality in reducing pain during the procedure. Secondary objectives will be assessed using the same outcome measures as primary objectives. This study will attempt to expand the use of SmileyScope virtual reality goggles, which have already been proven to reduce procedural pain in the pediatric population.

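### One satisfaction scale is set for every survey question, but the three closed items about VR ask about likelihood or helpfulness, so their answers would be ambiguous

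*Combined protocol and SAP*

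**What the plan says.** Section 6 lists five post-procedure satisfaction items, four closed and one free-text. The first closed item asks how satisfied the man was with the procedure. The other three are:

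- "If your urologist was using VR, would you be more or less likely to have the procedure"
- "If your urologist was using VR, how likely would you be to recommend them to a friend undergoing the same procedure"
- "How helpful was VR in managing your vasectomy today"

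The response rule is "All questions will be answered via a 5-point Likert Scale as below". The labels are graded by satisfaction, with 5 the most satisfied, 1 the least, and 3 labelled "Neither Satisfied nor Dissatisfied". A further code, 0, stands for "Not applicable / Decline to Answer".

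The survey has two stated uses. Section 2 (Objectives) sets the primary objective, to "assess the feasibility of using virtual reality goggles", and adds: "Feasibility will be further measured via subjective post-procedure satisfaction surveys". Section 5 (Research Procedures) also uses the survey as a further assessment of how well the goggles manage intraoperative pain.

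**The concern.** A response label should answer the question above it. A degree of satisfaction does not answer how likely or how helpful. If the form follows section 6, a man must translate the label for himself, and the analyst cannot tell afterwards which translation he used.

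The one item that fits its labels is about the procedure as a whole. The three that do not fit are the ones about VR. The mismatch therefore falls on the part of the survey most relevant to the feasibility of VR. Questionnaires in Spanish are also planned (Non-English Speaking Subjects, under section 16), so the same labels could be carried into both languages.

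**Working it through.** **The plan's own figure.** The plan gives no figure for the survey. Its one design figure is 162 men, 54 per group (section 5, Study Design). With effect size 0.25, alpha 0.05, power 0.8, 3 groups and 1 covariate, the ANCOVA F test has numerator df 2, denominator df N − 4 and noncentrality N × 0.25². The smallest N is 158 (power 0.802), or 159 with equal groups (0.805). At N = 162 the power is 0.813. The stated figure is reproduced closely, and no survey item enters it.

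**Items against labels (section 6).**

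| Closed item | Asks about | Mentions VR | Satisfaction labels fit |
|---|---|---|---|
| 1. Satisfaction with the procedure | Satisfaction | No | Yes |
| 2. More or less likely to have it | Likelihood (change) | Yes | No |
| 3. Likely to recommend | Likelihood | Yes | No |
| 4. Helpfulness of VR | Helpfulness | Yes | No |

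Counts: 3 of 4 closed items do not match, and these are 3 of the 3 that mention VR. The free-text item is left out of the count.

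**What each mismatch does.**

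- Item 2 is two-sided and needs a midpoint meaning that VR would make no difference. The listed midpoint expresses neutral satisfaction. A 3 could mean no effect of VR on the decision, or neutrality about the procedure or about VR.
- Item 3 asks for a likelihood. The labels give an order from favourable to unfavourable but no likelihood.
- Item 4 asks for a degree of helpfulness. A satisfaction label could be read as rating VR or the vasectomy. This is the weaker example, because the question names VR.

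**Is the rule repaired elsewhere?** Sections 2 and 5 name the survey without response options. Section 7 (Data Management) describes reporting only as a correlation between pain scores and physiological data. The provision for Spanish questionnaires gives no options. No likelihood or helpfulness labels appear anywhere in the documents.

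**Code 0.** The scale is called 5-point and its labels run from 1 to 5, so 0 is evidently a non-response code. No sentence says so, and none says which arms contribute to the helpfulness summary.

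**The case against.** The strongest objection is that section 6 is a list of data points, not the instrument. Its rule, read literally, also covers the free-text comment, which cannot be rated from 1 to 5. It is therefore loosely drafted and weak evidence of what men will see. This stands as a condition on the point: the form is not in the documents and may carry other options. It does not remove the point, because the protocol text as written sets one scale for all items.

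A second objection is that the labels run from favourable to unfavourable, so most men can answer by position. This stands, and it is why the answers are ambiguous rather than meaningless.

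A third is that the survey is supplementary for both of its uses. This stands too, and it limits the weight.

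Three stronger readings are tempting, and the documents do not support them:

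- **Three quarters of the survey is lost.** A reader might compute 4 × 162 = 648 closed answers, 3 × 162 = 486 under mismatched labels, and 486/648 = 75%. That only restates 3 of 4 at full response. It shows no bias and does not count misreadings.
- **A third of the helpfulness ratings come from men who had no VR (54/162).** The helpfulness item is not restricted to the VR arms, but code 0 gives no-VR men a valid reply. If all 54 use it, the figures above become 432 of 594 (72.7%), which is still only an item count.
- **A third of the answers to the two conditional VR items (108/324) are flawed because they are hypothetical for controls.** Those questions are conditional by their wording. Asking them of controls is not an error and has nothing to do with the labels.

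**Conclusion.** The point holds at minor weight. As written, section 6 puts satisfaction labels under three questions that do not ask about satisfaction, and these are all of the closed items that mention VR. The more-or-less-likely item is the clearest case.

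The size is a count of items: 3 of 4 closed items and 3 of 3 about VR. How many men would misread the labels cannot be estimated from the documents. The conclusion assumes that the form follows section 6.

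A reader might infer that the primary objective is compromised, or that new between-arm tests of the survey are needed. Neither follows. The pain scores, STAI-6, FitBit data and sample size do not depend on these labels. The documents plan no test of the survey, and which tests to run is a separate choice.

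**What to change.** In section 6, and in the English and Spanish questionnaires if they carry the same options:

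1. Keep the satisfaction options for the first item only.
2. Give the more-or-less-likely item five options from much less likely to much more likely, with no difference as the midpoint.
3. Give the recommendation item five options from very unlikely to very likely.
4. Give the helpfulness item five options from not at all helpful to extremely helpful, and summarise it in the two VR arms only.
5. State that code 0 is missing and lies outside the 1–5 score.

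The cost is a minor amendment. Any answers already collected under the old options should be reported separately, which leaves fewer answers on the new options for those three items. If the patient form already has item-specific options, the only change needed is to correct section 6 so that it matches the form.

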## 5) Procedures Involved

### Study Design

Patients will be randomized into one of three groups (interactive virtual reality, static virtual reality, and no virtual reality). Randomization sequence will be generated using a validated random number generator, and allocation concealment will be achieved via opaque envelope.

To ensure adequate power, the intended sample size has been calculated using the ANCOVA statistical test. Using G\*Power 3.1.9.4 software, a medium effect size 0.25, alpha 0.05, power 0.8, 3 groups and 1 covariate, the required sample size is 162 patients (54 patients per group, 1:1:1 ratio). No loss to follow up is anticipated.

All patients will be asked to wear the FitBit Versa 3 in the waiting room before the procedure. Patients randomized into one of the two virtual reality groups will be asked to wear the virtual reality goggles in the procedure room before the vasectomy. Before and after the procedure, a survey will be used to assess anxiety. Before the procedure, patients will also be asked to complete a pain scale survey to quantify baseline pain. After the procedure, patients will complete a pain scale survey to quantify their post-procedure pain. Physiologic data will be extracted from the FitBit device before, during, and after the vasectomy.

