## 8) Risks to Subjects

### Adverse Events and Serious Adverse Events

An adverse event will be defined as any event that may harm the subject or require the subject to seek medical attention, and a serious adverse event will be defined as adverse events that require the subject to seek medical attention and may be life threatening.

Adverse events include dizziness, nausea, vomiting, or falls during or immediately after wearing the VR headset.

A serious fall during or immediately after wearing the VR headset constitutes a serious adverse event. Seizures constitute a serious adverse event. However, this is highly unlikely, as the VR scenarios developed do not present the flashing visual stimuli associated with seizures. In addition, patients with epilepsy and other seizure disorders will be excluded from the study.

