### **14) Provisions to Protect the Privacy Interests of Subjects**

The study will be monitored by the PI to ensure appropriate study conduct, including obtaining proper access to data/specimens, compliance with the HIPAA Privacy Rule, compliance with University of Miami policy, and adhering to the plans outlined in the protocol for all study procedures, abstracting and recording data, data and/or specimen security and maintenance, and

data accuracy and integrity. Any adverse events, deviations, protocol exception requests, potential unanticipated problems involving risks to subjects or others, or other events will be submitted to the IRB in accordance with IRB reporting policy.

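### Dizziness, nausea, vomiting and falls are not collected systematically in the no-VR arm, so symptom counts will not be comparable between VR and no VR

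*Combined protocol and SAP*

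**What the plan says.** Section 5 (Study Design) randomises patients to three groups: "interactive virtual reality, static virtual reality, and no virtual reality". The allocation is 1:1:1 with 54 per group, and only the two VR groups wear goggles.

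Section 6 lists the data to be collected at the clinic visit, before the procedure and after it. The one safety item is "Adverse effects associated with goggles". The text with it is about the headset: patients may take it off, effects should then resolve, and "Most common adverse effects include dizziness and nausea".

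Section 8 opens with a definition that depends on neither arm nor device: "An adverse event will be defined as any event that may harm the subject or require the subject to seek medical attention". It then gives examples: "Adverse events include dizziness, nausea, vomiting, or falls during or immediately after wearing the VR headset". A serious fall counts as a serious adverse event under the same headset condition; a seizure counts without it.

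Section 14 adds a reporting route that is not limited by arm: "Any adverse events, deviations, protocol exception requests, potential unanticipated problems involving risks to subjects or others, or other events will be submitted to the IRB". The Section 6 satisfaction survey has a free-text comment item, also not limited by arm.

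No section describes a symptom question put to all arms, an adverse event form for the no-VR arm, or an analysis of adverse events by arm. Section 7 names only the correlation of pain scores with physiological data.

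**The concern.** Section 3 treats the device as investigational in this population. Dizziness and nausea, its expected effects, can also come from an operation on an awake patient or from anxiety. A concurrent control arm is the natural means of telling these causes apart, and the trial has one. As written, however, the plan prompts for these symptoms in the arms that wear goggles and relies on unprompted reporting in the arm that does not.

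If the counts were later set side by side, part of any difference would reflect how hard staff looked. In the VR arms, someone would have to decide case by case, knowing the allocation, whether a symptom belonged to the goggles. The information cannot be recovered reliably afterwards, because patients go home after the procedure.

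**Working it through.** **The plan's own figure.** The sample size is 162 (Section 5: ANCOVA, f = 0.25, alpha 0.05, power 0.80, 3 groups, 1 covariate). With numerator df 2, denominator df N − 3 − 1 and noncentrality N × f², the smallest N with power 0.80 is 158, or 159 as a multiple of 3. At N = 162 the noncentrality is 162 × 0.0625 = 10.125 and the power is 0.813. The figure is reproduced to within 3%. The point does not depend on it; only the arm sizes are used below: 54 no VR and 2 × 54 = 108 VR.

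**The passages side by side.**
- Section 6 data item: effects of the goggles. It has nothing to record where no goggles are worn.
- Section 8 examples: tied to headset wear.
- Section 8 definition: applies to all arms, but prompts nobody to ask about symptoms.
- Section 14 IRB route: applies to all arms, but passes on events that have already been noticed.
- Section 6 free text: not limited by arm, but unprompted and not about symptoms.

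Systematic collection is therefore planned only where goggles are worn. Elsewhere it is incidental.

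**Size.** The documents give no symptom rates, so every rate below is an assumption.

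*1. Background events.* Suppose symptoms unrelated to VR occur at the same rate p in all arms.
- VR arms: 108 × 0.02 = 2.2 to 108 × 0.10 = 10.8 expected events.
- The chance of at least one among VR patients is 1 − 0.98^108 = 0.887 at 2% and above 0.9999 at 10%.
- No-VR arm: 54 × 0.02 = 1.1 to 54 × 0.10 = 5.4 expected events, which may go unrecorded.

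*2. Limiting case: no control event is recorded (0 of 54) although the true rates are equal.* A two-sided Fisher test against 108 VR patients gives p = 0.053 with 8 VR events and p = 0.030 with 9, so 9 or more are needed for p < 0.05. The binomial probability of reaching that is:

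| True rate, all arms | Expected no-VR events missed | Probability of a false signal against VR |
|---|---|---|
| 2% | 1.1 | 0.00 |
| 5% | 2.7 | 0.09 |
| 10% | 5.4 | 0.76 |
| 15% | 8.1 | 0.99 |

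This is an upper bound on the distortion, since some control events may surface, and the plan does not call for such a test.

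*3. Precision if all arms are asked.* The half-width of the 95% confidence interval for VR minus no VR at a common rate p is 1.96 × √[p(1 − p)/108 + p(1 − p)/54] = 1.96 × √[p(1 − p)/36].
- p = 0.05: 1.96 × √(0.0475/36) = 0.071.
- p = 0.10: 1.96 × √(0.09/36) = 0.098.

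*4. Power if all arms are asked* (Fisher, two-sided 0.05, 54 against 108):

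| No VR | VR | Power |
|---|---|---|
| 5% | 10% | 0.12 |
| 5% | 15% | 0.42 |
| 5% | 20% | 0.75 |
| 5% | 25% | 0.93 |
| 10% | 20% | 0.32 |
| 10% | 30% | 0.84 |

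In these scenarios, 80% power needs a difference of about 20 percentage points.

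**The case against.** The best defence is that the plan does not shut control events out. The definition in Section 8 is neutral as to arm, its list of symptoms gives examples and sets no limit, Section 14 sends any adverse event to the IRB, and the free-text item is open to all. All of this stands. A reader might infer that the no-VR arm must record zero events by construction; the documents do not support that. They also contain no case report form, so what the control arm's form will hold is not known. What remains is that none of these routes asks a control patient about dizziness or nausea, so mild symptoms would probably be missed.

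A reader might also infer that every symptom in a VR patient will be booked to the goggles. The text does not say so. The Section 6 item leaves room for a decision on association, and resolution after headset removal would give some within-patient evidence of cause.

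A third tempting inference is that the feasibility result is biased against VR. Section 2 measures feasibility by pain, physiological data, anxiety and satisfaction. Tolerability is not among these, and no comparison of adverse events between arms is planned, so no planned estimate is biased.

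Finally, the fix buys limited precision: at the assumed 5% and 10% rates, the half-width is about as large as the rate itself. That is correct, and it is why the comparison should be presented as descriptive.

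**Conclusion.** The point holds as a gap in safety data collection. Following the plan as written, these symptoms are collected systematically in VR patients and only incidentally in the no-VR arm. Counts would not be comparable between VR and no VR, and effects of the procedure or of anxiety could not be separated from effects of the device. The primary and secondary objectives are untouched, and interactive and static VR can still be compared because both arms wear goggles.

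The size rests on assumed rates. In the limiting case of no recorded control events, the distortion is negligible at 2%, modest at 5% and serious at 10%. Collecting the item in all arms would make the comparison fair but would not give power for modest differences. The change is worth making because it is cheap and the data are hard to obtain later.

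**What to change.** - In Section 6, replace the goggles item with one checklist (dizziness, nausea, vomiting, fall, other). Ask it of all three arms over the same window, for example from entering the procedure room until leaving, whatever the suspected cause.
- Record relation to the goggles as a separate field, for VR patients only.
- In Section 8, word the example events so that they apply to all arms, in line with the general definition that precedes them.
- In Section 7, add a table of counts with 95% confidence intervals by randomised arm, with the VR minus no-VR difference, labelled as descriptive and without a formal test.

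The cost is a few tick-boxes for 54 control patients and one table. The downside is that more adverse events will be reported overall.
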